3.4. Test Hypothesis and P Value Justification

Not applicable since no inferential statistics will be provided for this PMR. Whenever it is appropriate, 2-sided 95% confidence intervals will be provided for estimates.

3.5. Procedures for Handling Missing Data

No missing data imputation will be performed for safety parameters. However, patients with missing infusion stop time will be assigned an imputed stop time in order to derive the efficacy endpoints (See [Section 3.3.2](#) for details).

3.6. Analysis Center

Both studies are multicenter studies; hence, investigative center will be identified as part of the unique patient identification. Data summaries will not be prepared by center unless data warrant.

3.7. Definitions and Derived Variables

3.7.1. Baseline

Baseline will be defined as the last measurement before the start of the first infusion. Baseline records will be marked for all efficacy and safety (laboratory, ECG, vital signs, and clinical signs and symptoms) records in the database.

There was a situation where a baseline metHb measurement had the exact time of the first dose infusion start time; the data were queried and confirmed.

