2.2. Data Collection

2.2.1. HQF-METHB-2018001

Protocol HQF-METHB-2018001 is designed to be a low-burden minimal-risk **Observational Study**; data collection largely is by passive chart review, with follow-up by telephone or postal mail and/or using medical records where applicable. At some participating study sites, follow-up of acquired methemoglobinemia patients is standard care or part of quality improvement efforts, and some study sites are operating under a full waiver of consent / assent, based on local IRB approvals.

To minimize risk and qualify for the most streamlined study procedures, the **Observational Study** is electronic source (paper forms are not required) and the study data are de-identified to the HIPAA Safe-Harbor standard. Notably, the Safe-Harbor method involves collection of relative “study days” (eg, “Study Day 1, 12:45”) rather than absolute “calendar days” (eg, December 31, 2019, 12:45). Significantly, the “study day” safe-harbor format does not restrict any of the proposed analyses. In our proposed analyses, a pseudo enrollment date was created for each patient when the patient’s case was registered in the database.

To support intuitive and consistent presentation of the data, Study Day 1 Hour 0 is defined as the day and time of the completion of the first methylene blue infusion, and the timing of all study

measurements is presented as the relative time elapsed from this reference point. Thus, a negative relative time indicates that an event/assessment occurred prior to the first infusion completion time, whereas a positive relative time indicates that an event/assessment occurred after the first infusion conclusion time.

To gain understanding about all real-world cases of acquired methemoglobinemia treated with ProvayBlue™, and to encourage more sites to participate by making the enrollment criteria less restrictive, enrollment of a “Secondary Treated Group” was included in the Observational Study. That is, this study groups enrolled patients into two subgroups: Primary cases or Secondary cases.

All primary cases must fulfill the following requirements:

1. Baseline metHb $\geq 30\%$, OR
2. Documented signs or symptoms of methemoglobinemia with subsequent assay of methemoglobin levels above the institutional upper limit of normal (ULN). For these patients, response to the question ‘Were there any signs or symptoms judged to be clinically associated with the acquired methemoglobinemia?’ must be a ‘Yes’

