3.3.2. Relative Time of Efficacy Endpoints

A relative time frame will be used to display and to summarize efficacy assessments.

The stop time of the first ProvayBlue™ infusion will be used to derive relative time (hours) for each post infusion metHb and vital signs assessment. After all efforts are made to ensure the capture of infusion start and stop time, when the stop time is missing, the following imputation rule will be used to impute the missing stop time.

Missing stop time will be imputed with the median infusion duration of the efficacy population. Mathematically, this imputation rule can be expressed as

$$\text{Stop time} = \text{start time} + \text{median infusion duration}$$

Where the median infusion duration is derived from all patients in the efficacy population.

Relative time of an assessment (hours) = Time of assessment – Time of stop time of 1st Infusion.

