5.1.1. MetHb Level at 1-hour Post Dosing

The timing of postdosing metHb level assays is inconsistent in clinical practice and may not be obtained until hours after the conclusion of first dose infusion in the emergency department. It should be noted that, consistent with such practice, the Observational Study does not have a prespecified schedule for metHb postdosing collection. MetHb level at 1-hour postdosing will be derived using linear interpolation. This method will be referred to as backward linear interpolation if the first postdosing metHb was after 1 hour, or forward linear interpolation if the first postdosing metHb was before 1 hour. This method will be mathematically expressed as follows.

Step 1: calculate rate of metHb change per minutes)

$$= (\text{metHb_1} - \text{baseline}) / \text{time of metHb_1 in minutes}$$

Step 2:

$$\text{metHb_1hr} = \text{baseline} + 60 * [(\text{metHb_1} - \text{baseline}) / (\text{time of metHb_1 in minutes})]$$

where

- baseline = baseline metHb defined as the last metHb before the first dose of study drug)
- metHb_1 = first post treatment metHb observation
- constant (60) converted the time units from minutes to hours

For example, a patient has metHb of 74.40 at baseline and 15.70 at 70 minutes postdosing. The estimated metHb_1hr is 24.08571.

Percent change from baseline (PCHG) at 1-hour post dosing can be estimated as follows.

$$\text{PCHG (\%)} \text{ at 1-hour post dosing} = 100 * [(\text{metHb_1} - \text{baseline}) / \text{time of metHb_1 in minutes}] / \text{baseline}$$

The PCHG for the above example is -67.63%.

$$\text{PCHG at 1-hour} = 100 * \{ [60 * (15.7 - 74.4) / 70] / 74.4 \}$$

Due to the mathematical property of this derivation, a patient could never achieve 50% reduction at 1-hour post dosing if the first postdosing metHb was taken after 2 hours. Hence, this derivation will be applied only to those patients who had first postdosing metHb before 2 hours.

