5.1.4. Individual Profile of metHb

Individual profiles of metHb over time will be prepared for each patient. All metHb assessments will be included. The profile will flag if the patient is a Primary case or a Secondary case.

The change from baseline in metHb will also be graphically presented, showing the change from baseline by time (hours) for each patient (Figure 14.2.1.3) as illustrated in Figure 1.

Figure 1: Example of Individual Profile of metHb Before and After Treatment

Hour 0 is when the first dose of ProvayBlueTM infusion is completed and the dotted vertical reference line is 1 hour after the end of infusion.

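### The SAP's 1-hour metHb and T50 interpolations place a pre-infusion baseline at the end of infusion, which can change responder status in Table 14.2.1.1 in either direction

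*SAP*

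**What the plan says.** Four statements in the SAP have to be read together.

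- **Baseline** (Section 3.7.1): "Baseline will be defined as the last measurement before the start of the first infusion".
- **Time origin** (Section 2.2.1, HQF-METHB-2018001): "Study Day 1 Hour 0 is defined as the day and time of the completion of the first methylene blue infusion". Under Section 3.3.2 the stop time of the first infusion "will be used to derive relative time (hours) for each post infusion metHb and vital signs assessment". The note to Figure 1 in Section 5.1.4 agrees: "Hour 0 is when the first dose of ProvayBlueTM infusion is completed".
- **1-hour value** (Section 5.1.1): "MetHb level at 1-hour postdosing will be derived using linear interpolation". The rate is the change from baseline to the first post-treatment value, divided by the time of that value in minutes. The 1-hour value is baseline plus 60 times this rate. Section 5.1.2 uses the same rate for T50, the time at which metHb has fallen by half.
- **First sample** (Section 5.1.1): "metHb_1 = first post treatment metHb observation". The derivation is limited to first samples taken before 2 hours. No lower limit on the time is given.

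The dosing note to SAP Table 2 gives an infusion length of 5 to 30 minutes. The interpolated values feed Table 14.2.1.1, which counts patients with at least a 50% reduction at 1 hour and reports predicted T50 (Section 5.1.3).

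**The concern.** On the SAP's time axis the baseline sample was drawn at minus d minutes or earlier, where d is the infusion duration. The formulas put it at zero. Any fall during the infusion is then credited to the minutes after it, so the fitted slope is always too steep relative to a line that begins at infusion start.

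The protocol's primary endpoint is a 50% reduction within 1 hour of the first dose (Protocol Section 7.2.1). The SAP's own primary measure uses the first available sample, whenever it was taken (Section 3.3.1). Table 14.2.1.1 is therefore the planned summary that estimates 1-hour response for patients not sampled at 1 hour. Enrolment was 7 + 24 = 31 patients and the table covers a subset, so one reclassified patient moves the rate by more than 1/31 = 3.2 percentage points. If the anchor is wrong, a patient's status can depend on infusion length.

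**Working it through.** **Notation.** b = baseline, m = first post-treatment value, t = minutes from infusion end to that sample, d = infusion duration, f = (b − m)/b. The range of d (5 to 30) comes from the dosing note. The example's own infusion duration is not given.

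**Reproducing the SAP example** (b = 74.4, m = 15.7, t = 70):

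- 1-hour value: 74.4 + 60 × (15.7 − 74.4)/70 = 24.09
- Percent change: 100 × (24.09 − 74.4)/74.4 = −67.6%
- T50: 37.2/(58.7/70) = 44.36 min

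All three match the SAP. I use the forms that give its stated results. As printed, the percent-change formula lacks the factor 60 and the T50 formula has an extra one; that is a separate matter.

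**Re-anchoring baseline at infusion start** (time −d):

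- 1-hour value = b + (60 + d)(m − b)/(t + d)
- T50 from infusion end = (b/2)(t + d)/(b − m) − d

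| SAP example | 1-hour metHb | Change | T50 from infusion end |
|---|---|---|---|
| As written | 24.09 | −67.6% | 44.4 min |
| d = 5 | 23.53 | −68.4% | 42.5 min |
| d = 15 | 22.61 | −69.6% | 38.9 min |
| d = 30 | 21.57 | −71.0% | 33.4 min |

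**Direction.** The predicted fractional fall is 60f/t as written and (60 + d)f/(t + d) re-anchored. The first minus the second is f·d·(60 − t)/[t(t + d)]. It is positive for t below 60, zero at 60 and negative above. For T50, re-anchored minus as written is d(0.5/f − 1), which is zero only at f = 0.5.

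**Smallest observed fall that counts as a 1-hour response:** t/120 as written, 0.5(t + d)/(60 + d) re-anchored.

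| t (min) | As written | d = 5 | d = 15 | d = 30 |
|---|---|---|---|---|
| 15 | 12.5% | 15.4% | 20.0% | 25.0% |
| 30 | 25.0% | 26.9% | 30.0% | 33.3% |
| 60 | 50.0% | 50.0% | 50.0% | 50.0% |
| 90 | 75.0% | 73.1% | 70.0% | 66.7% |
| 110 | 91.7% | 88.5% | 83.3% | 77.8% |

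**Changes of status at d = 30** (illustrative patients):

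- 30% fall at 30 min: 60 × 0.30/30 = 60.0% as written; 90 × 0.30/60 = 45.0% re-anchored. T50 is 50 and 70 min.
- 70% fall at 90 min: 60 × 0.70/90 = 46.7% as written; 90 × 0.70/120 = 52.5% re-anchored. T50 is 64.3 and 55.7 min.

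**The 2-hour limit.** The SAP argues that a patient first sampled after 2 hours could never reach a 50% fall at 1 hour. That follows from t/120 ≤ 1. Re-anchored, the limit is t ≤ 120 + d, or 125 to 150 min.

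**The case against.** **The re-anchored line is also an assumption.** Baseline may have been drawn some time before the infusion began, and the fall need not be linear from the first drop. The package insert in the protocol (Section 12.2) calls the exposure-response relationship unknown. This stands: the differences above are between two straight lines, not measured errors. But infusion start fits the SAP's own baseline definition better. It needs metHb to be stable only up to the start, whereas the written formula needs it stable through the infusion as well. Section 3.7.1 also records a confirmed baseline timed exactly at infusion start.

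**The flips are hypothetical.** They use d = 30, the end of the permitted range, and no distribution of durations is given. The 30% fall at 30 minutes remains a responder at d = 5 (65 × 0.30/35 = 55.7%). This stands too: the documents show that flips are possible, not how many would occur.

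**A sample during infusion.** Section 2.2.1 says that "a negative relative time indicates that an event/assessment occurred prior to the first infusion completion time", so a reader might infer that such a sample will enter the formula and reverse the result. With b = 40 and m = 30 at t = −10, the formula gives 40 + 60 × (−10)/(−10) = 100, a fall reported as a rise. The documents do not support this as an expected outcome. Section 3.3.2 refers to post-infusion assessments, the efficacy set in Section 3.2 requires a sample after infusion, and nothing shows that a mid-infusion sample exists. Section 3.7.3 describes the same set more loosely, by a postbaseline value. What remains is a missing explicit rule.

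**Conclusion.** The mismatch is in the SAP text: a value taken before infusion start is used as the value at infusion end. Relative to a line from infusion start, the predicted 1-hour fall is overstated for first samples before 60 minutes, unaffected at 60 and understated between 60 and 120. T50 shifts by d(0.5/f − 1) minutes. The effect is largest for early samples after long infusions. In the SAP's example it is modest and conservative: 0.8 to 3.4 percentage points, and 1.8 to 11.0 minutes on T50.

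Two stronger readings are not supported. One is that the main efficacy result is compromised. The Section 3.3.1 primary measure and Table 14.2.1.2 use the first observed value, the individual profiles plot all metHb assessments, and Section 3.4 plans no inferential statistics. The other is that the method inflates efficacy in general. Its direction depends on sampling time, and for first samples after 60 minutes it works against the drug.

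The conclusion rests on d between 5 and 30 minutes, stable metHb from the baseline draw to infusion start, and the linear fall that the SAP already assumes. The correction is worth making because Table 14.2.1.1 is small and its responder count can change.

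**What to change.** 1. In Section 5.1.1, use metHb_1hr = baseline + (60 + d)(metHb_1 − baseline)/(t + d).
2. In Section 5.1.2, use T50 = (baseline/2)(t + d)/(baseline − metHb_1) − d, and state that it is counted from infusion end.
3. Require t > 0 for metHb_1. This also guards against t = 0, where the written formula divides by zero.
4. Keep the 2-hour entry limit if wished, so that the population and title of Table 14.2.1.1 do not change, but correct its mathematical reason: the limit becomes 120 + d minutes.

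The cost is a small change to the SAP text and programs. Section 3.3.2 already seeks start and stop times.

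The fix assumes metHb is stable from the baseline draw to infusion start. Where the stop time is missing, the imputed duration still sets the 1-hour target, although it drops out of the slope because t + d is simply time since infusion start. Reliance on imputation therefore falls. As an illustration, take a 25% fall sampled 50 minutes after start, with the stop imputed at 5 to 30 minutes. As written, the predicted fall runs from 60 × 0.25/45 = 33.3% to 60 × 0.25/20 = 75.0%. Re-anchored, it runs from 65 × 0.25/50 = 32.5% to 90 × 0.25/50 = 45.0%.

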3.7.2. Patient Groups by Methemoglobinemia Suspected Causative Agent

Patients are grouped in 2 subsets based on their methemoglobinemia suspected causative agent: Group 1 includes all patients that metHb was associated with Dapsone use, and Group 2 includes all non-Dapsone-caused metHb. The differentiation is primarily based on

- the frequency with which Dapsone is expected to be identified as the causative agent for inducing methemoglobinemia, and
- the long half-life of Dapsone and its metabolite dapsone hydroxylamine, which likely results in ongoing production of metHb through the acute treatment phase, in contrast to short-acting inciting agents such as amyl nitrate, where normal physiologic conversion of metHb to hemoglobin may begin shortly after exposure.

Patient group will be used for data summary tables.

3.7.3. Patient Groups by Methemoglobinemia Severity

In the Observational Study, all enrolled patients are classified as either a Primary case or a Secondary case (See Section 2.2.1). The patients marked as Primary cases are more severe cases and the data are monitored, whereas the patients marked as Secondary cases are less severe and, aside from verification of the inclusion criteria, data in these cases are not monitored.

All patients from the Interventional Study are classified as Primary cases.

Secondary cases are excluded from the efficacy analysis set (the efficacy analysis set includes the Primary cases that have baseline and at least 1 postbaseline metHb measurement, See Section 3.2). Although all patients are included in the safety analysis set, due to the difference in data monitoring between the Primary and Secondary cases, the safety data will be analyzed twice: one set will include patients from the Primary cases, and the second set will include all patients.

Patient type (Primary vs Secondary) will be clearly flagged in the individual patient data listings as well as the profile figures.

4. DATA SUMMARIES

It is anticipated that the pooled results will be presented as a series of individual patient descriptive narratives with limited statistical analysis. The narratives will also identify issues in individual patient past medical history, exposures, and comorbidities that may impact the consideration and interpretation of “normal” vital signs and related parameters.

When appropriate, summary tables will also be prepared that will include descriptive statistics, such as sample size, mean, standard deviation, minimum, median, and maximum for continuous variables and number (%) of patients for categorical variables. Data summaries will provide descriptive statistics for all patients, patients with possible causative agent of Dapsone, and patients with non-Dapsone causative agents.

All data in the pooled database will have a patient level data listing.

4.1. Disposition

A summary table (Table 14.1.1) will provide frequency counts for all patients enrolled, patients in the safety analysis set, patients in the efficacy analysis set, and 10-day posttreatment status (alive, deceased, unknown, lost to follow-up). A summary of disposition will be provided overall and by protocol (PVP-2016003 vs HQF-METHB-2018001).

Disposition data will be provided as a data listing (Listing 16.2.1).

4.2. Demographics and Baseline Characteristics

The demographic summary will include descriptive statistics for age, sex, race, ethnicity, weight, height, and body mass index (BMI) at baseline.

Baseline characteristics and patient population characteristics will also include the following study information:

- 1) Patient setting before first presentation
- 2) Acquired methemoglobinemia diagnosis:
 - a. Diagnosis by
 - b. Diagnosis setting
 - c. Suspected causative agent
 - d. Exposure to agent
- 3) Methemoglobinemia assessments and treatment at baseline:
 - a. Any signs and symptoms judged to be clinically associated with the acquired methemoglobinemia (yes/no)?
 - b. Are co-oximetry results available from the index hospitalization (yes/no)?

- c. Are arterial blood gas results available from the index hospitalization (yes/no)?
- d. Baseline metHb level
- e. Was ProvayBlue™ administered before enrollment to the study (yes /no)?
- f. Were any other treatments employed to mitigate the acquired methemoglobinemia (yes/no)?

Demographics and baseline characteristics will be tabulated for the safety analysis set (Tables 14.1.2.1 and 14.1.2.2) and efficacy analysis set (Table 14.1.2.3) with no formal inferential tests. Demographic data will be provided as a data listing (Listing 16.2.2).

4.3. Medical History

All medical history data captured will be listed without any formal summaries (Listing 16.2.3).

4.4. Protocol Deviations

Any clinically relevant protocol deviation will be identified and described in the clinical study report without any formal summary.

4.5. Treatment Compliance

Not applicable.

4.6. Prior and Concomitant Medications

All prior and concomitant medications will be listed without any formal summaries (Listing 16.2.6).

5. EFFICACY ANALYSIS

Efficacy data listings by individual patient will be prepared for all efficacy endpoints, including the observed value and derived variables (Listing 16.2.8, Listing 16.2.9, Listing 16.2.13). Efficacy analysis will be based on the patients included in the efficacy analysis set.

5.1. Treatment Effect on metHb

MetHb measurements can be obtained via co-oximetry from either arterial or venous blood gas specimens. Data will be pooled and sorted by time of measurement taken for analysis. The following parameters will be derived to aid discussion of treatment effect on the metHb reduction.

5.1.1. MetHb Level at 1-hour Post Dosing

The timing of postdosing metHb level assays is inconsistent in clinical practice and may not be obtained until hours after the conclusion of first dose infusion in the emergency department. It should be noted that, consistent with such practice, the Observational Study does not have a prespecified schedule for metHb postdosing collection. MetHb level at 1-hour postdosing will be derived using linear interpolation. This method will be referred to as backward linear interpolation if the first postdosing metHb was after 1 hour, or forward linear interpolation if the first postdosing metHb was before 1 hour. This method will be mathematically expressed as follows.

Step 1: calculate rate of metHb change per minutes)

$$= (\text{metHb_1} - \text{baseline}) / \text{time of metHb_1 in minutes}$$

Step 2:

$$\text{metHb_1hr} = \text{baseline} + 60 * [(\text{metHb_1} - \text{baseline}) / (\text{time of metHb_1 in minutes})]$$

where

- baseline = baseline metHb defined as the last metHb before the first dose of study drug)
- metHb_1 = first post treatment metHb observation
- constant (60) converted the time units from minutes to hours

For example, a patient has metHb of 74.40 at baseline and 15.70 at 70 minutes postdosing. The estimated metHb_1hr is 24.08571.

Percent change from baseline (PCHG) at 1-hour post dosing can be estimated as follows.

$$\text{PCHG (\%)} \text{ at 1-hour post dosing} = 100 * [(\text{metHb_1} - \text{baseline}) / \text{time of metHb_1 in minutes}] / \text{baseline}$$

The PCHG for the above example is -67.63%.

$$\text{PCHG at 1-hour} = 100 * \{ [60 * (15.7 - 74.4) / 70] / 74.4 \}$$

Due to the mathematical property of this derivation, a patient could never achieve 50% reduction at 1-hour post dosing if the first postdosing metHb was taken after 2 hours. Hence, this derivation will be applied only to those patients who had first postdosing metHb before 2 hours.

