3.2. Analysis Population

The following analysis sets will be identified for data summary.

Enrolled Analysis Set: All patients who sign the informed consent or otherwise meet all local enrollment criteria for the study are considered to have enrolled.

Safety Analysis Set: The safety set will include all enrolled patients who are treated with at least 1 ProvayBlue™ infusion dose. The safety analysis set will be used for safety data summary. Specifically, the safety population will include all treated patients from the Interventional Study and the Observational Study.

Efficacy Analysis Set: The efficacy analysis set includes all safety analysis set patients who have at least 1 metHb assessment before and after ProvayBlue™ infusion and who are Primary cases. This analysis set will be used for efficacy endpoint evaluation.

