5.1.2. Time When metHb Level Reached 50% Reduction

To estimate the time when a 50% reduction would be obtained, the following linear interpolation will be applied.

$T_{50} \text{ (minutes after first dose)} = (\text{baseline}/2) / [60 * (\text{baseline} - \text{metHb}_1) / \text{time of metHb}_1 \text{ in minutes}]$

T50 for the above example is 44 minutes.

$$T_{50} = (74/2) / \{ [(74.4 - 15.7) / 70] / 74.4 \} = 37.2 / 0.838571428 = 44.36$$

The units for T50 will be converted to hours by $T_{50} / 60$ in the dataset.

Due to the mathematical property of this derivation, a patient could never achieve 50% reduction at 1-hour post dosing if the first postdosing metHb was taken after 2 hours. Hence, this derivation will be applied only to those patients who had first postdosing metHb before 2 hours.

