5.1.3. Summary of metHb

The treatment effect on metHb will be evaluated based on change in metHb from baseline. Because of the wide range in assessment times, the summary table will include only 2 time points: Baseline (last metHb before treatment) and predicted metHb at 1-hour posttreatment. The table will provide descriptive statistics for the observed metHb level, change from baseline, and percent change from baseline, including sample size, mean, standard deviation, and 2-sided 95% confidence intervals for the mean, minimum, median, and maximum. Number (%) patients with $\geq 50\%$ metHb reduction 1 hour posttreatment will be identified. (Table 14.2.1.1). This table will also include predicted time when metHb 50% reduction would occur and time when the first metHb is obtained.

[figure not shown]
A second summary table (Table 14.2.1.2) will provide metHb level descriptive summary at baseline and metHb level of the first follow-up posttreatment for all patients in the efficacy analysis set. In this table, the level of metHb at the first follow-up and time when the first follow-up metHb is taken will be summarized.

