7. ABLE OF CONTENTS OF PLANNED DATA SUMMARIES

7.1. Summary Tables

Number	Type	Title	Analysis Set
14.1.1	Table	Patient Enrollment and Analysis Set and Post Treatment Follow-up Status	Enrolled Analysis Set
14.1.2.1	Table	Demographics and Baseline Characteristics	Safety Analysis Set - Primary Cases
14.1.2.2	Table	Demographics and Baseline Characteristics	Safety Analysis Set - All Patients
14.1.2.3	Table	Demographics and Baseline Characteristics	Efficacy Analysis Set
14.2.1.1	Table	Predicted MetHb Level 1 Hour Post First Infusion in Patients with First MetHb Drawn Within 2 Hours of Dosing	Efficacy Analysis Set
14.2.1.2	Table	Summary of 1st Follow-up MetHb Level Regardless When the Assessment Was Taken	Efficacy Analysis Set
14.2.1.3	Figure	Individual Profile of Change from Baseline in MetHb Before and After Treatment	Safety Analysis Set - All Patients
14.2.2.1	Table	Summary of Vital Signs at Baseline and Within 2 Hours Post First Infusion	Efficacy Analysis Set
14.2.2.2	Figure	Individual Profile of Change from Baseline in Vital Signs Before and After Treatment	Safety Analysis Set - All Patients
14.2.3.1	Table	Summary of Methemoglobinemia Signs and Symptoms Before and After Treatment	Efficacy Analysis Set
14.2.3.2	Figure	Scatter Plots Showing Individual Profile of Methemoglobinemia Signs and Symptoms Before and After Treatment	Efficacy Analysis Set
14.3.1.1	Table	Study Drug Infusions	Safety Analysis Set - Primary Cases
14.3.1.2	Table	Study Drug Infusions	Safety Analysis Set - All Patients
14.3.2.1.1	Table	Topline Summary of Treatment Emergent Adverse Event	Safety Analysis Set - Primary Cases
14.3.2.1.2	Table	Topline Summary of Treatment Emergent Adverse Event	Safety Analysis Set - All Patients
14.3.2.2.1	Table	All TEAE by Preferred Term Displayed the Most Commonly Reported Event First	Safety Analysis Set - Primary Cases
14.3.2.2.2	Table	All TEAE by Preferred Term Displayed the Most Commonly Reported Event First	Safety Analysis Set - All Patients
14.3.2.3.1	Table	All TEAE by SOC and Preferred Term	Safety Analysis Set - Primary Cases
14.3.2.3.2	Table	All TEAE by SOC and Preferred Term	Safety Analysis Set - All Patients
14.3.2.4.1	Table	All TEAE by SOC, Preferred Term and Intensity	Safety Analysis Set - Primary Cases
14.3.2.4.2	Table	All TEAE by SOC, Preferred Term and Intensity	Safety Analysis Set - All Patients
14.3.2.5.1	Table	All TEAE by SOC, Preferred Term and Relationship to Study Drug	Safety Analysis Set - Primary Cases

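### SAP 5.1.1–5.1.2: the printed general PCHG and T50 formulas are each 60-fold too small against the SAP's own example, and the predicted 1-hour response in descriptive Table 14.2.1.1 depends on when the first sample was drawn

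*SAP*

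**What the plan says.** SAP 5.1.1 derives a 1-hour metHb value for each patient from two points, baseline and the first post-treatment observation. It gives as its reason that "the Observational Study does not have a prespecified schedule for metHb postdosing collection". A first sample after 1 hour is carried back along the line. A first sample before 1 hour is carried on, which the SAP calls "forward linear interpolation if the first postdosing metHb was before 1 hour". The derivation applies only when the first sample came before 2 hours.

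The worked example is a fall from 74.40 to 15.70 at 70 minutes, with a 1-hour value of 24.08571. The SAP adds: "The PCHG for the above example is -67.63" (per cent). In SAP 5.1.2, "T50 for the above example is 44 minutes", and a further step follows: "The units for T50 will be converted to hours by" dividing by 60.

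The results go into Table 14.2.1.1, "Predicted MetHb Level 1 Hour Post First Infusion in Patients with First MetHb Drawn Within 2 Hours of Dosing". For that table SAP 5.1.3 says that the number and percentage with at least 50% "metHb reduction 1 hour posttreatment will be identified". It is drawn from the efficacy set, which requires "at least 1 metHb assessment before and after ProvayBlue™ infusion and who are Primary cases". The primary count in SAP 3.3.1 is separate and uses the first available post-treatment value.

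**The concern.** The general formulas in SAP 5.1.1 and 5.1.2 do not give the SAP's own answers, so a programmer who codes them literally would produce wrong values for every patient.

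Separately, a line through two points makes the 1-hour result depend on when the second point was taken. The protocol's primary endpoint is a 50% fall within 1 hour of the first dose (Protocol 7.2.1). Table 14.2.1.1 is the only planned table whose text names a 1-hour count of that kind; the text for Table 14.2.1.2 lists only level and time. Readers are likely to take the count as the answer to the protocol's question.

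**Working it through.** **Inputs** (SAP 5.1.1 example): baseline 74.4, metHb_1 15.7, t = 70 min. Time zero is the end of the first infusion (SAP 3.3.2). Rate = (15.7 − 74.4)/70 = −0.838571 per minute.

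**The stated figures reproduce.**
- metHb_1hr = 74.4 + 60 × (−0.838571) = 24.0857
- PCHG = 100 × 60 × (−0.838571)/74.4 = −67.63%
- T50 = 37.2/0.838571 = 44.36 min = 0.739 h

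**The printed general formulas do not.**
- PCHG has no factor 60: 100 × (−0.838571)/74.4 = −1.13%. With a fractional fall f, this form reaches −50% only if t ≤ 2f, so only for a draw within 2 minutes.
- T50 is labelled minutes but has 60 in the denominator: 37.2/(60 × 0.838571) = 0.739, which is really hours. The later division by 60 turns it into 0.0123 h.

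The worked T50 line also shows 74/2 and a stray division by 74.4. Taken literally, 37/(0.838571/74.4) = 3,282.7. These two items may come from text extraction and should be checked against the source PDF; the conclusion does not rest on them.

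**The responder rule, with formulas corrected.** If f is the observed fractional fall at minute t, the predicted 1-hour fall is f × 60/t. It is at least 50% if and only if f ≥ t/120. Predicted metHb is negative if and only if f > t/60.

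| First sample (min) | Observed fall needed to count as a 1-hour responder |
|---|---|
| 15 | 12.5% |
| 30 | 25% |
| 45 | 37.5% |
| 60 | 50% |
| 75 | 62.5% |
| 90 | 75% |
| 119 | 99.2% |

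The same observed 60% fall is predicted as 120% if drawn at 30 minutes, 60% at 60 and 40% at 90. Close to 1 hour the rescaling is small: 60/55 = 1.09 and 60/50 = 1.20.

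**Constructed cases.**
- Negative level: 40% falling to 25% at 20 min gives 40 + 60 × (25 − 40)/20 = −5%.
- Observed value overridden: baseline 40%, 35% at 10 min, 26% observed at 60 min. The rule uses only the 10-minute sample: 40 + 60 × (35 − 40)/10 = 10%, a 75% fall. The observed fall is (40 − 26)/40 = 35%.
- T50 when metHb rises: 30% to 33% at 40 min gives 15/[(30 − 33)/40] = −200 min. If metHb_1 equals baseline, the denominator is zero. No rule covers either case.

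**Can early draws happen?** Protocol 8.3 places H1 at 1 hour after the infusion, but footnote l of SAP Table 2 asks for metHb within 1 hour of its end, and the Observational Study has no schedule. Actual draw times are not given.

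**Weight of one patient.** Enrolment was 7 + 24 = 31 (SAP 1), so the denominator is at most 31. One reclassified patient moves the percentage by at least 100/31 = 3.2 points; if the denominator were 10, by 10.0 points.

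**The case against.** The formula error largely corrects itself: Steps 1 and 2, the worked PCHG line and all three stated answers are right, so running the example would expose a literal coding. The projection is an openly described approximation in a table titled as predicted. The SAP says the derivation serves discussion, admits a mathematical limit, cuts off at 2 hours and plans no inference (SAP 3.4). Readers also get the time of the first sample, the observed first follow-up level in Table 14.2.1.2, and individual profiles with a 1-hour reference line.

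All of that stands and lowers the weight. It does not make the printed formulas correct. The 2-hour cut-off only removes draws for which the bar exceeds 100%; the sliding bar below 2 hours remains, and the early side is not addressed.

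A reader might infer three stronger things that the documents do not support.
- *That the main result is wrong.* The SAP 3.3.1 count does not use the projection or these formulas.
- *That the method favours the drug.* The bar is lenient before 60 minutes and strict after, so the net direction depends on unknown draw times.
- *That a decay model can size the misclassification.* The documents give no such model. The answer would also depend on when the decline is assumed to start: time zero is the end of infusion (SAP 3.3.2), baseline precedes its start (SAP 3.7.1), and infusions run 5–30 minutes (Protocol 8.1).

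**Conclusion.** The point holds in three parts.

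(a) The printed general PCHG and T50 formulas are each 60-fold too small on the SAP's own example. This is certain from the SAP alone, and recoverable because the stated answers and the metHb_1hr formula are correct.

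(b) The 1-hour count in descriptive Table 14.2.1.1 applies a response bar of t/120 and so mixes draw time with drug effect. This is exact algebra and needs no model. What the SAP calls forward interpolation is extrapolation; it can give negative metHb and can override a value observed at 60 minutes.

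(c) T50 is undefined or negative when metHb does not fall.

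How often (b) and (c) occur, and their net effect on the percentage, cannot be computed from the documents.

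**What to change.** 1. Correct the formulas. PCHG = 100 × 60 × [(metHb_1 − baseline)/t]/baseline. T50 (min) = (baseline/2)/[(baseline − metHb_1)/t], divided by 60 once for hours. Check the worked T50 line against the source PDF.
2. For 1-hour response, count an observed fall of at least 50% at or before 60 minutes. Otherwise use an observed sample in a stated window around 60 minutes. Otherwise interpolate between the samples that bracket 60 minutes. Do not use samples taken after a second dose.
3. Do not extrapolate forward. Patients with only early samples and less than a 50% fall are listed as *not determined*, kept in the denominator, with observed value and time.
4. Where the bracketing pair is baseline and a sample after 60 minutes, the t/120 bar remains. Label the result as dependent on draw time and show the observed fall and its time. Do not offer low and high counts as bounds, because metHb may rebound (Protocol 11.3). For instance, 40% falling to an unsampled 18% at 60 minutes and back to 24% at 110 is a true 55% fall at 1 hour but an observed 40% fall. That is below both the 50% bar and the 110/120 = 91.7% bar.
5. Report T50 only where a 50% fall was observed, interpolated between the samples that bracket the crossing. List the others as *not reached*.

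Keep the present derivation, with corrected formulas, as a secondary display. Record the change as made after enrolment closed and after metHb data from 13 patients had been summarized to the agency (SAP 1).

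Cost: SAP wording, some reprogramming and a data-aware change to document; no new data. Some patients become *not determined*, and the table is less tidy.
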